## 6. General Issues for Statistical Analysis

All data collected in the study will be listed, ordered by site, treatment, patient number and, where applicable, chronological order of the assessment. Visit date is not needed to be included in the listings, day numbers will be included where appropriate.

Other derived variables (e.g. change from baseline values) that are calculated for analysis purposes or to aid interpretation of the data will be included in the data listings.

### 6.1 Statistical Definitions and Algorithms

#### 6.1.1 Conventions for treatment/visit naming

In all tables, listings and figures, the treatment arms will be referred to and labelled as per [Table 2](#)  
Study treatments

**Table 2** Study treatments

Endpoint	Actual Treatment	Treatment Label (Table column/Figure legend)	Sorting order in listings, column order in tables
Efficacy	Pooled Placebo	Placebo	3
Safety,	5 mg/kg/day Placebo	Placebo 5 mg/kg	3
Demographics	15 mg/kg/day Placebo	Placebo 15 mg/kg	4
and Baseline	Pooled Placebo	Placebo	5
All	5 mg/kg/day GWP42003-P	GWP42003-P 5 mg/kg	1
All	15 mg/kg/day GWP42003-P	GWP42003-P 15 mg/kg	2

For safety tables where placebo is split by dosage, an additional Pooled Placebo column will be included.

In all tables, listings and figures, the study visits will be referred to and labelled as per [Table 3](#).

**Table 3**      **Study Visits**

Actual Visit	Visit Label
Visit 1: Screening	Screening
Visit 2: Day 1, baseline visit	Day 1
Visit 3: Day 8	Day 8
Visit 4: Day 15	Day 15
Visit 5: Day 29	Day 29
Visit 6: Day 57	Day 57
Visit 7: Day 85	Day 85
Visit 8: Day 127	Day 127
Visit 9: Day 169	End of Treatment
Visit 10: Day 179	End of Taper
Visit 11: Day 207	Safety Follow-Up

No derivation will be used for visits; data will be tabulated and listed according to the visit it was recorded under in eCRF.

#### **6.1.2    Baseline**

For all efficacy endpoints Visit 2 will be used as the baseline observation for all calculations. The baseline value for the symptom diary will be the mean of the symptom diary scores prior to first dose.

For all safety endpoints, the last non-missing observation recorded prior to the first drug administration will be used as the baseline observation for all calculations.

#### **6.1.3    Last Visit**

The last visit for efficacy endpoints assessed at clinic visits is defined as the last scheduled visit at which a patient's last evaluation (up to Visit 9/end of treatment visit/any other last visit) is performed.

#### **6.1.4    Study Periods**

Treatment period: Day 1 to Day 169.

##### **For 15 mg/kg/day group only:**

Titration period: Day 1 to Day 14

Maintenance period: Day 15 to Day 169.

#### **6.1.5    Day Numbering**

The first day of treatment (Day 1) will be the date on the 'First IMP Dose' eCRF.

Any days prior to Day 1 will be numbered relative to this day and calculated as:

$$\text{Date} - (\text{Date of Day 1})$$

to give Day  $-1, -2, -3$  etc.

Any days post Day 1 will be calculated as:

$$1 + \text{Date} - (\text{Date of Day 1})$$

### 6.1.6 Multiple Comparisons

Multiple comparisons with regards to primary/key secondary/secondary endpoints are detailed in Efficacy Analysis [section 8](#).

### 6.1.7 Handling of Dropouts or Missing Data

Every effort has been made to minimize missing data for this trial. The patient reported outcomes will be completed by the patient's primary caregiver on electronic devices. These assessments have been set up in such a way that the caregiver cannot proceed to the next question if they have not entered a response for the current question. In addition, on the off chance that the device does not function correctly, paper alternatives of the assessments are available.

#### 6.1.7.1 Handling of Missing Data for Efficacy Endpoint (Primary, Secondary and Exploratory)

If a questionnaire has subscales then the missing items in a subscale can be imputed as the mean of the non-missing items in that subscale, provided that at least half of the items in the subscale were answered. If more than half the items in the subscale are missing then the missing items will be imputed as LOCF.

If a questionnaire does not have subscales (eg MBA-9, CSHQ single item scale) the missing items will be imputed using LOCF.

##### 6.1.7.1.1 SF-36

The SF-36 assessment will be scored by the QualityMetric Health Outcomes Scoring Software 5.0 ([Maruish, 2011](#)) which assumes that the response to a missing item in a particular scale is the same as the mean of the responses to the scale's answered items. This approach cannot be used to estimate item responses on the physical functioning scale due to the hierarchical nature of the items included in this scale. If items on the physical functioning scale are missing, the QualityMetric Health Outcomes Scoring Software v5.0 estimates the PF score using item response theory. If any SF-36 is logged as completed by an alternative caregiver, it will be counted as missing.

##### 6.1.7.1.2 CHQ-PF50

[Appendix 5](#) describes the methods of handling missing data for the CHQ-PF50 health scales.

##### 6.1.7.1.3 Adverse Events

Missing and/or incomplete dates for AEs will be imputed in a manner resulting in the earliest onset or the longest duration during the treatment period, while ensuring that the start date is not after the stop date, i.e. missing start dates will be imputed as the first day of the month/first month of

the year and missing stop dates will be imputed as the last day of the month/last day of the year, while ensuring that the start date is not after the stop date. Upper and lower limits of imputation will be date of Visit 2 and date of Visit 9, and events occurring on date of Visit 2 will be assumed post-IMP as per [Section 6.1.9.1](#) Stop dates will not be imputed if the AE is ongoing.

The imputation method will be used to determine treatment emergence and time to onset/resolution of an AE, and imputed dates/times will not be presented in AE outputs.

A worst-case approach will be followed in the event of missing severity or causality data. If the severity is missing, ‘Severe’ will be imputed. If causality data is missing for a treatment emergent AE (TEAE), ‘Yes’ will be imputed for the question ‘Plausible relationship to study medication’.

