12.6 Reporting Procedures for All Adverse Events

All AEs (including SAEs) occurring during the trial will be reported on the running logs in the AE section of the eCRF. This includes all events from the time following screening (Visit 1) up to and including the post-trial follow-up visit (Visit 11), whether or not attributed to IMP and observed by the investigator or patient.

For the patient's expected seizure types, these do not routinely require documentation as AEs. However, any worsening, including change in the pattern or severity of seizures should be documented in the eCRF if deemed to meet the definition of an AE, in the investigator's opinion.

Any AE which meets SAE criteria should still be reported as a SAE.

The following information will need to be provided for all AEs:

A) Adverse Event (Diagnosis or Syndrome if Known, or Signs and Symptoms)

Where the investigator cannot determine a diagnosis, signs or symptoms should be recorded in the AE section of the eCRF. Once a diagnosis has been determined the AE section of eCRF must be updated to reflect the diagnosis in replacement of the original symptoms. In circumstances where only a provisional diagnosis is possible (working diagnosis), the eCRF must be updated to reflect the provisional diagnosis in replacement of the original symptoms. In some circumstances it may be relevant for the investigator to include the symptoms alongside the diagnosis in the verbatim event description.

Study Code: GWND18064

EudraCT Number: 2018-003370-27

Clinical Protocol 4.1, 07Jul2020 (duplicate synopsis removed)

However, the diagnosis (full or provisional) should be clearly stated, e.g., fever and malaise due to respiratory tract infection.

B) Adverse Event Start Date and Stop Date

The start and stop dates of the event must be provided. All AEs require these fields to be completed in full. Partial dates or missing dates are not normally acceptable and significant effort must be undertaken to obtain any unknown information. If a precise date is not known an estimated date should be provided instead. When a complete date cannot be given, record as much information as possible (i.e., month and year or, in exceptional circumstances, just year). When the actual start date becomes known the eCRF must be updated to replace the previously recorded date.

C) Outcome

The outcome of the event must be recorded accurately and classified into 1 of the following categories:

- Recovered.
- Recovered with sequelae.

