#### **6.1.9.1 Adverse events**

A TEAE is defined as an AE with a start date on or after the first dose of IMP. If an AE has a partial start date and it is unclear from the partial date (or the stop date) whether the AE started prior to or post first dose of IMP then the AE will be considered treatment emergent. If the start date of the AE is the same as the date of first dose of IMP then the AE will be considered treatment emergent.

A TEAE will be considered treatment-related if the plausibility relationship to IMP is recorded on the eCRF as ‘yes’. If the data on plausibility relationship to IMP is missing then the TEAE will be considered treatment-related.

A TEAE will be considered leading to permanent discontinuation of IMP (leading to withdrawal) if the action taken with IMP is recorded on the eCRF as ‘trial medication stopped’ or the outcome is recorded on the eCRF as ‘patient died’.

A treatment-related TEAEs leading to withdrawal is a TEAE leading to permanent IMP

discontinuation and considered treatment-related as per above definition.

A TEAE will be considered leading to IMP temporary discontinuation if the action taken with IMP is recorded on the eCRF as 'trial medication interrupted'.

A TEAE will be considered leading to permanent IMP dose reduction excluding permanent discontinuation if the action taken with IMP is recorded on the eCRF as 'dose reduced'.

An AE will be considered fatal if the outcome is recorded on the eCRF as 'patient died'.

The time to first onset of AE will be calculated for TEAEs as:

Start date of AE – Date of first dose of IMP + 1

The time to AE resolution will be calculated for TEAEs as:

Stop date of AE – Start date of AE + 1

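### The SAP confines imputed AE dates to Visit 2 through Visit 9, so clearly pre-dose partial start dates become treatment-emergent and partial stop dates after Visit 9 cannot be imputed coherently

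*SAP*

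**What the plan says.** **Imputation rule (SAP 6.1.7.1.3).** A missing start day or month becomes the first of the period and a missing stop becomes the last. Dates are "imputed in a manner resulting in the earliest onset or the longest duration during the treatment period", and "while ensuring that the start date is not after the stop date". The bounds are: "Upper and lower limits of imputation will be date of Visit 2 and date of Visit 9". The words upper and lower are in the reverse order to the two visits. The dates have a use beyond display: "The imputation method will be used to determine treatment emergence and time to onset/resolution of an AE". Ongoing AEs receive no imputed stop date.

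**Treatment emergence (SAP 6.1.9.1).** "A TEAE is defined as an AE with a start date on or after the first dose of IMP", with no end date. The conservative default is conditional: "If an AE has a partial start date and it is unclear from the partial date (or the stop date) whether the AE started" before or after first dose, the event counts as treatment-emergent. Time to resolution is stop minus start plus 1, for all TEAEs.

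**Listings (SAP 9.1).** A partial date that is clearly before first dose is listed as pre.

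**Collection window (Protocol 12.6).** "This includes all events from the time following screening (Visit 1) up to and including the post-trial follow-up visit (Visit 11"). Attribution to treatment is not a condition for recording.

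**The concern.** The imputation window is narrower than the collection window at both ends, and the imputed dates feed two derived quantities.

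At the early end, sections 6.1.7.1.3 and 6.1.9.1 can classify the same record differently. An AE known to have begun in a month before the Visit 2 month could be counted in the TEAE tables and shown as pre in the listing. If its causality is also missing, 6.1.7.1.3 imputes a plausible relationship for a TEAE. Protocol 12.5 says events starting before first dose should be considered not causally related.

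At the late end, the taper and follow-up periods are where withdrawal-type events, named in SAP Appendix 2, would be expected. Time to resolution for such events can come out zero, negative or artificially short.

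The analysis is descriptive (SAP 8), so AE tables are among the main outputs. Two programmers following this text could produce different TEAE counts.

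**Working it through.** The plan gives no figure to reproduce; this is a date rule applied step by step.

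**Window.** Visit 9 is Day 169, Visit 10 is 10 days later and Visit 11 is 28 days after that (Protocol 9.1.1.8 and 9.1.2.1): 169 + 10 + 28 = Day 207. So 207 − 169 = 38 days lie beyond the upper bound. Before the lower bound lies a baseline of 14 to 28 days, up to 28 + 6 = 34 with the Visit 2 window (Protocol 9.1.1.2).

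**Worked patient.** Visit 2 and first dose on 10 Jun 2020; Visit 9 is 168 days later, 25 Nov 2020; Visit 11 is 206 days later, 2 Jan 2021.

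*1. Start dates, day unknown, no known stop date before Visit 2*

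| Recorded start | Imputed under 6.1.7.1.3 | Result by imputation | Result under 6.1.9.1 |
|---|---|---|---|
| May 2020 | 1 May, lifted to 10 Jun | TEAE on Day 1 | Clearly pre-dose: not a TEAE |
| Jun 2020 | 1 Jun, lifted to 10 Jun | TEAE on Day 1 | Unclear: TEAE |

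Only the first row is in conflict. To see how often that row would arise, assume month-only start dates, true onset uniform over the baseline days, and Visit 2 falling on each of 365 consecutive days from 1 January 2020. An onset *j* days before Visit 2 falls in an earlier month when *j* is at least the day-of-month of Visit 2.

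| Baseline length | Clearly pre-dose (conflict) | Same month as Visit 2 (no conflict) |
|---|---|---|
| 14 days | 23.0% | 77.0% |
| 28 days | 46.0% | 54.0% |
| 34 days | 55.4% | 44.6% |

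A hand check for 28 days: *j* runs from 1 to 27 with mean 14, and 14 / 30.5 = 45.9%. These are shares of month-only pre-dose onsets, not of all AEs.

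*2. Stop dates, AE resolved, day unknown*

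- **Onset after Visit 9.** The imputed stop is at most Visit 9 and the start at least Visit 9 + 1. So stop − start + 1 ≤ V9 − (V9 + 1) + 1 = 0 in every case under a literal cap. Example: onset 5 Dec, stop recorded as Dec 2020, imputed 31 Dec and capped at 25 Nov; duration −10 + 1 = −9 days. If the ordering rule overrides the cap, the natural result is stop = start, a duration of 1 day. With a Visit 11 cap the stop is 31 Dec and the duration 26 + 1 = 27 days.
- **Category.** Either outcome falls in the class of 7 days or fewer in SAP 9.1. If all onset and stop pairs within Days 170 to 207 were equally likely, 496 of 741 (66.9%) would truly last longer than 7 days.
- **Onset before Visit 9, stop in a later month.** Onset 20 Nov, stop recorded as Dec 2020, capped at 25 Nov: 5 + 1 = 6 days. The earliest stop the record allows is 1 Dec (11 + 1 = 12 days) and the latest is 31 Dec (41 + 1 = 42 days). The imputed value is shorter than the recorded month permits. With true stops uniform over Days 170 to 207 and month-only dates, the imputed stop falls outside its own recorded month in 61.3% of cases.

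**The case against.** **Ambiguous starts are handled as intended.** A reader might infer that every partial-date pre-dose event is wrongly made treatment-emergent. The documents do not support that. Where the known month includes first dose, 6.1.9.1 makes the event a TEAE by an explicit conservative rule, and the Visit 2 floor carries it out. A known stop date before Visit 2 also keeps an event pre-dose, through the ordering rule. This stands and limits the early-end problem to clearly pre-dose records. Even there, 6.1.9.1 is the more specific rule and SAP 9.1 plans separate pre-treatment AE outputs, so a careful programmer might never apply the floor. But 6.1.7.1.3 says that imputation determines emergence, and no precedence is stated.

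**Negative durations are forbidden by the same paragraph.** It is tempting to present a negative duration as what the SAP prescribes. It is what the cap alone gives; the ordering rule prohibits it. The supportable statement is that the two rules cannot both be met for onsets after Visit 9.

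**The aim is duration within the treatment period.** A reader might say that the cap defeats an aim of longest duration. The stated aim is limited to the treatment period, Day 1 to Day 169 (SAP 6.1.4), so truncation at Visit 9 is consistent with it. What remains is that time to resolution is calculated for all TEAEs, including later ones, and that a capped stop can contradict its own recorded month.

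**No bias towards either arm is built in.** The rule is identical for active and placebo. Late onsets are TEAEs in any case and stay in the open-ended onset class beyond 22 weeks.

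**Small reach.** Complete dates and ongoing AEs are unaffected. Patients who move straight into the extension need no Visit 10 or 11. Protocol 12.6 discourages partial dates, and imputed dates are not displayed. All of this stands.

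**Conclusion.** The concern holds in a narrow form and is minor. Read literally, SAP 6.1.7.1.3 conflicts with 6.1.9.1 and 9.1 for partial start dates that are clearly before first dose, and it sets an unsatisfiable pair of conditions for resolved AEs that start after Visit 9 with a partial stop date. It can also place a stop date outside its recorded month when the AE began before Visit 9.

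The consequence at the early end is TEAE status. At the late end it is time to resolution only. The number of affected records cannot be derived, because neither document gives a rate of partial dates; the percentages above are conditional on a month-only date and on uniform timing. With a descriptive analysis and partial dates discouraged, the overall effect is probably small.

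**What to change.** Amend SAP 6.1.7.1.3 as follows:

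1. State that treatment emergence is decided by 6.1.9.1 alone. Apply the Visit 2 (first-dose) floor to an imputed start only when the known part of the date cannot exclude onset on or after first dose. Leave clearly pre-dose partial dates as pre-treatment.
2. Cap imputed stop dates at Visit 11 or last contact instead of Visit 9. In the calculation above this removes every non-positive duration for onsets after Visit 9 (100% to 0%).
3. Put upper and lower in the order of the visits they refer to.

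Do not move the start-date floor to Visit 1. In the worked patient, a start recorded as Jun 2020 would become 1 Jun, which is before first dose, against 6.1.9.1. If it were still kept as a TEAE, time to onset would be 1 Jun − 10 Jun + 1 = −8 days, which fits no onset class in SAP 9.1.

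SAP 6.1.7.1.4 borrows this rule for concomitant medications while 6.1.9.2 says missing dates are not replaced, so that cross-reference should be checked in the same edit.

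The cost is about two sentences and trivial programming, with no new data.

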#### **6.1.7.1.4 Concomitant Medication**

Missing concomitant medication dates will be handled in a similar fashion as described for AEs in [Section 6.1.7.1.3](#).

#### **6.1.8 Pooling of Sites**

As there are expected to be relatively few patients per site, the site will not be taken into account in the analyses. Therefore the question of pooling of sites does not arise.

#### **6.1.9 Derived Variables**

For derivations of the efficacy variables, see [Section 8](#). The following additional derived and computed variables have been initially identified as important for the analyses to be performed for this trial.

In case additional derived variables may be required: the SAP will not be amended for additional variables that are not related to the primary or secondary endpoints. Any additional derived or computed variables will be identified and documented in the SAS programs that create the analysis files. If the SAP is not amended, further derivations related to the primary and secondary endpoints will be described in the CSR.

#### **6.1.9.1 Adverse events**

A TEAE is defined as an AE with a start date on or after the first dose of IMP. If an AE has a partial start date and it is unclear from the partial date (or the stop date) whether the AE started prior to or post first dose of IMP then the AE will be considered treatment emergent. If the start date of the AE is the same as the date of first dose of IMP then the AE will be considered treatment emergent.

A TEAE will be considered treatment-related if the plausibility relationship to IMP is recorded on the eCRF as ‘yes’. If the data on plausibility relationship to IMP is missing then the TEAE will be considered treatment-related.

A TEAE will be considered leading to permanent discontinuation of IMP (leading to withdrawal) if the action taken with IMP is recorded on the eCRF as ‘trial medication stopped’ or the outcome is recorded on the eCRF as ‘patient died’.

A treatment-related TEAEs leading to withdrawal is a TEAE leading to permanent IMP

discontinuation and considered treatment-related as per above definition.

A TEAE will be considered leading to IMP temporary discontinuation if the action taken with IMP is recorded on the eCRF as 'trial medication interrupted'.

A TEAE will be considered leading to permanent IMP dose reduction excluding permanent discontinuation if the action taken with IMP is recorded on the eCRF as 'dose reduced'.

An AE will be considered fatal if the outcome is recorded on the eCRF as 'patient died'.

The time to first onset of AE will be calculated for TEAEs as:

Start date of AE – Date of first dose of IMP + 1

The time to AE resolution will be calculated for TEAEs as:

Stop date of AE – Start date of AE + 1

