Transaminase elevations should be medically managed by the investigator either by reducing the IMP dose as described above or, following discussion with the medical monitor, by reducing concomitant medications judged to be causing the elevation (as per [Section 8.2](#)). Dose adjustments should be discussed with the GW medical monitor. For potential cases of drug-induced liver injury see [Section 12.8](#).

Patients will escalate IMP to the target dose level for their dose group over a period of up to 2 weeks depending on the target dose (e.g., no titration is required to 5 mg/kg/day while titration to 15 mg/kg/day takes 2 weeks [weekly increments of 5 mg/kg/day] as indicated in [Table 8.1.2-1](#)). Following escalation patients will remain at their assigned target dose level for the duration of the maintenance period of the trial.

Study Code: GWND18064

EudraCT Number: 2018-003370-27

Clinical Protocol 4.1, 07Jul2020 (duplicate synopsis removed)

Table 8.1.2-1 Dose Escalation Regimen

Day	Dose GWP42003-P (mg/kg/day)*
1-7	5
8-14	10
15	15

* IMP is to be taken twice daily. Total daily doses are shown. The placebo group will take matching volumes of placebo.

After completion of dosing, patients who do not immediately enter the OLE study (under a separate protocol) at Visit 9 will have their dose of IMP tapered gradually, an average of 10% of per day, over a period of 10 days (the taper period may be shorter if the patient enters the OLE during the taper period). Patients who reach the minimum single dose volume of 0.1 mL should remain at that dose until they complete the taper period. A taper schedule will be provided for each patient.

Patients who discontinue from treatment early should also taper the IMP (unless continued dosing is inadvisable, e.g., due to an AE). The decision whether to taper IMP or not will be left to the investigator's clinical judgment.

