9.1.2 Telephone Visits (Safety Follow-Ups)

9.1.2.1 Visits 3 (Day 8), 4 (Day 15), 11 (Day 207)

Visits 3 and 4 will occur 7 and 14 days after randomization (Visit 2), respectively.

Visit 11 will occur 28 days after Visit 10 (or Visit 9 if the patient did not taper) for patients who do not enter the OLE trial (under a separate protocol) or who withdraw from the trial early.

A visit window of \pm 3 days from the scheduled visit date is permitted, except for Visit 11, where a window of + 3 days is permitted, but it is preferred that the visit is performed on the scheduled visit day where possible.

Telephone visits will be conducted and information regarding adherence to the dosing regimen (except for Visit 11), AEs, and changes to concomitant medications will be reviewed by a delegated personnel (the site investigator need only be involved if necessary, e.g., if any concerns are raised during the call). The weekly symptom diary will be reviewed (except for Visit 11).

Visit 11 constitutes the last scheduled safety follow-up. The purpose of the visit is to ascertain the status of AEs continuing after cessation of IMP or any new AEs commencing after discontinuation. All causally-related AEs that result in a patient's premature termination from the trial or are present at the end of the trial should be followed up until a satisfactory resolution occurs; that is, until the AE resolves or is considered clinically insignificant, or until an investigator is satisfied that the AE is not related to IMP and needs no further investigation.

Study Code: GWND18064

EudraCT Number: 2018-003370-27

Clinical Protocol 4.1, 07Jul2020 (duplicate synopsis removed)

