- AE (including clinically significant laboratory result) which, in the opinion of the investigator, would compromise the continued safe participation of the patient in the trial.
- Did not meet eligibility criteria.
- Any evidence of use of drugs of abuse or drug diversion.
- Suicidal ideation or behavior during the treatment period.

Patients who discontinue IMP should have their dose of IMP gradually reduced (10% each day) over a period of 10 days, beginning at the time the decision is made to discontinue (unless inadvisable due to an AE). Patients should continue in the trial and continue to complete trial assessments and visits as per protocol. Patients who discontinue IMP and complete tapering of IMP prior to the completion visit, do not need to attend an End of Taper visit.

Should a patient request or decide to withdraw from the trial, all efforts must be made to complete and report the observations as thoroughly as possible up to the date of withdrawal. Patients withdrawing due to an AE should be followed up according to [Section 12.7](#). All information should be reported on the applicable eCRF pages (refer to [Section 9.2](#)). All assessments required at the withdrawal visit should be conducted if possible. If the tapered dose is administered, patients should return for Visit 10, if possible. Wherever possible, a safety follow-up visit should take place 28 days from the date of last dose of IMP (refer to [Section 9.1.2](#)). If the withdrawing patient declines to give a reason for withdrawal of consent, the investigator must respect the patient's wishes.

Study Code: GWND18064

EudraCT Number: 2018-003370-27

Clinical Protocol 4.1, 07Jul2020 (duplicate synopsis removed)

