12 ADVERSE EVENT REPORTING

12.1 Definitions

12.1.1 Adverse Event

For the purposes of this trial an AE is defined as:

Any new unfavorable/unintended signs/symptoms (including abnormal laboratory findings when relevant), or diagnosis or worsening of a pre-existing condition, which occurs following screening (Visit 1) and at any point up to the post-treatment, final safety follow-up visit (Visit 11), which may or may not be considered to be related to the IMP. Any event that is the result of a trial procedure must be recorded as an AE.

Surgical/Investigational procedures are not AEs. The medical reason for the procedure is the AE. Elective hospitalizations for pre-trial existing conditions or elective procedures are not AEs. The exception may be if the patient has an AE during hospitalization which prolongs their scheduled hospital stay in which case it would be considered a SAE (refer to [Section 12.2](#)).

If reporting a fatal event, the SAE term should be the underlying cause of the death (e.g., disease or medical condition leading to death).

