13.6.3.2 Adverse Events

Adverse events will be coded according to the Medical Dictionary for Regulatory Activities dictionary.

A treatment-emergent adverse event (TEAE) is one that started, or worsened in severity or seriousness, following the first dose of IMP.

Descriptive presentations of TEAEs will be given by preferred term and SOC for the safety analysis set. The number of patients reporting at least 1 TEAE will be provided.

The following summaries will be produced as a minimum:

- All-causality TEAEs.

Study Code: GWND18064

EudraCT Number: 2018-003370-27

Clinical Protocol 4.1, 07Jul2020 (duplicate synopsis removed)

- Treatment-related AEs.
- All-causality TEAEs by maximal severity.
- All-causality serious TEAEs.
- Treatment-related serious TEAEs.
- TEAEs reported as leading to permanent cessation of IMP.
- Fatal TEAEs.

In the presentation of safety data, data from the GWP42003-P dose groups will be presented separately and compared with placebo. This will allow the possibility to explore any effects of the dose of IMP on safety endpoints.

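### Treatment-emergent AEs have a start but no end in SAP 6.1.9.1, and no planned AE table is anchored to the last dose, so on-drug, taper and off-drug onsets cannot be told apart in the tables

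*SAP*

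**What the plan says.** **Definition.** SAP 6.1.9.1: "A TEAE is defined as an AE with a start date on or after the first dose of IMP". Protocol 13.6.3.2 also sets only a start: "A treatment-emergent adverse event (TEAE) is one that started, or worsened in severity or seriousness, following the first dose of IMP". Neither document limits treatment emergence to a number of days after last dose.

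**Collection.** Protocol 12.1.1 counts an AE "at any point up to the post-treatment, final safety follow-up visit (Visit 11"), whether or not the patient is still dosed. Protocol 12.6 agrees. On patients who stop IMP early, Protocol 10 says: "Patients should continue in the trial and continue to complete trial assessments and visits as per protocol".

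**Periods.** SAP 6.1.4 gives "Treatment period: Day 1 to Day 169" and, for the 15 mg/kg/day arm, titration and maintenance periods. It defines no taper, follow-up or off-treatment period.

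**Tables.** The overall AE summary in SAP 9.1 separates only the titration period. The onset table counts days from first dose. Its last bounded row ends at Day 154, and the row after that is open-ended.

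**Listings.** SAP 9.1 plans listings with start and stop day relative to first dose and a treatment-emergence flag, plus a separate listing of events of special interest. Appendix 2 puts drug-withdrawal and rebound terms among those events.

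**The concern.** Readers take TEAE tables as a description of what happens on drug. Under the stated rule, a patient who stops in week 5 and stays in the trial contributes treatment-emergent events for the rest of the schedule, with nothing in the tables to show that the drug had been stopped. Events during the taper and the four weeks after it are likewise merged with events under full dosing.

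Two things are at stake. Background events from off-drug time sit in the same percentages as on-drug events, which can dilute a real difference from placebo. And although the SAP lists withdrawal terms as events of special interest, no planned table lines up onsets after dosing ends, which is where a withdrawal pattern would appear. The trial was discontinued and its analysis is descriptive, so these safety tables are a main part of its output.

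**Working it through.** **1. Reproduce the plan's own end point.** Inputs: treatment ends at Day 169 (SAP 6.1.4). Protocol 8.1.2 has the dose "tapered gradually, an average of 10% of per day, over a period of 10 days". Protocol 9.1.2.1 states: "Visit 11 will occur 28 days after Visit 10 (or Visit 9 if the patient did not taper").

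169 + 10 = 179 (Visit 10); 179 + 28 = 207 (Visit 11). This matches the scheduled Day 207 exactly. Day 207 is therefore the effective end of TEAE capture for a completer who tapers and does not enter the extension.

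**2. The last onset row for that completer.** Days 155 to 207 = 207 − 154 = 53 days.

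- Treatment: 169 − 154 = 15 days
- Taper: 179 − 169 = 10 days
- Off drug: 207 − 179 = 28 days

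Taper and follow-up make up 38 of 53 days (72%).

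**3. Early stoppers who stay on study.** Let L be the day of the last dose, including taper. Off-drug days to Visit 9 = 169 − L. Days more than 28 days after last dose = 169 − L − 28. The values of L are illustrations; the documents give no distribution of stopping times.

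| Last taper dose (L) | Off-drug days to Visit 9 | Of these, more than 28 days after last dose |
|---|---|---|
| Day 39 | 130 | 102 |
| Day 40 | 129 | 101 |
| Day 67 | 102 | 74 |
| Day 95 | 74 | 46 |

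For L = 40, 129/169 = 76% of the scheduled treatment period is off drug. Days after Visit 9 are left out, because the documents do not settle when such a patient has the safety follow-up. Protocol 9.1.2.1 counts 28 days from Visit 10, or from Visit 9 without a taper; footnote c of the schedule of assessments counts four weeks from last dose.

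**4. Where those days fall in the onset table.** For L = 40: 2 days in the Weeks 3–6 row (Days 41–42), 28 in each of the next four rows, and 15 up to Visit 9 in the last row. 2 + 4 × 28 + 15 = 129. All would be displayed as ordinary onset times after first dose.

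**5. Date imputation.** SAP 6.1.7.1.3 caps imputed AE dates at Visit 9, so a partially dated taper or follow-up event can be placed inside the treatment period. This adds to the mixing.

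**The case against.** The strongest reply is that the open window is deliberate and keeps the arms comparable. Patients who stop IMP and remain on study attend the same visits as those still dosing, so background events accrue over similar time in each arm. A reader might infer that off-drug events are added to the arm with more discontinuations; the documents do not support that, because such patients gain no extra observation time. Cutting the TEAE window at last dose plus 28 days would instead shorten observation in that arm and make crude percentages less comparable. This part stands, and it is why the existing summaries should stay.

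The affected group is also narrow. For a tapering completer, last dose plus 28 days is exactly Day 207, so that window would remove nothing. Patients who leave the trial are followed for about 28 days after last dose. Only early stoppers who stay are exposed to the months-long case, and there may be few of them.

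A reader might also infer that withdrawal events cannot be seen at all. That goes too far. The listings show start days, special-interest events have their own listing, final dose dates are on the eCRF (SAP 7.4), and the action-taken field has a category for patients no longer on IMP (Protocol 12.6). Manual separation is possible. The table shells are a separate document that was not available.

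Finally, the onset table partly adjusts its denominators to patients seen in each interval, treatment-related TEAEs are summarized separately, and no hypothesis test is affected. What remains after all this is that no table described in the SAP uses last dose as a reference point.

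**Conclusion.** The point holds as a gap in labelling and presentation. The rule treats events starting long after last dose as treatment-emergent, and the planned tables do not separate on-drug, taper and off-drug onsets. The size is clear for an individual (129 of 169 days off drug, 101 of them remote, for a last dose on Day 40) and for the last onset row (38 of 53 days for a tapering completer). The effect on TEAE percentages cannot be computed, because the number and timing of early stoppers are not given.

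The documents do not support reading this as a bias that inflates AE counts in one arm. A sponsor-wide stop shortens follow-up alike across randomized arms in expectation, so it does not by itself create such a bias either. The likely direction is dilution of a drug effect and loss of a visible post-dosing pattern. The 28-day mark is a conventional reference used here for illustration; no text in either document fixes it as an analysis window.

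**What to change.** - **Keep** the summaries of all events after first dose, so that the arms remain comparable.
- **Add to SAP 6.1.4 and 6.1.9.1** an on-treatment flag: onset from first dose to last dose including taper, plus a prespecified window (28 days, for example), or to the first extension dose if that is earlier. Define taper and post-treatment periods alongside it.
- **Repeat the overall TEAE summary** for flagged events.
- **Add one table by arm** of AEs with onset after the last full dose, covering taper and follow-up and including the Appendix 2 withdrawal terms.
- **Split the onset table** at each patient's end of treatment.
- **Optionally**, show patient-years beside the overall TEAE table. Follow-up is unequal after the trial was stopped, and patients going straight into the extension have no taper or follow-up.

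SAP 7.4 says that the final treatment-period dose and the final taper dose are recorded, and SAP 6.1.9.4 already uses the former. One detail needs a rule: Protocol 10 waives the end-of-taper visit for early stoppers who finish tapering before Visit 9. The SAP should name the source of their last taper dose, such as the daily dosing diary.

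The cost is SAP wording, a derived flag and one or two tables, with no new data. Counts in the post-dosing table will be small and should be read descriptively.
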